9. SAFETY DEFINITIONS, REPORTING, AND MONITORING

9.1. Obligations of Investigator

The investigator must promptly report to the IRB or EC all unanticipated problems involving risks to patients, according to local regulations. This may include death from any cause and all serious adverse events (SAEs) related to the use of the study drug. It is recommended that all SAEs be reported to the IRB or EC according to local regulations.

9.2. Obligations of Sponsor

During the course of the study, the sponsor will report in an expedited manner all SAEs that are both unexpected and at least reasonably related to the study drug (SUSAR), to the health authorities, EC/IRBs as appropriate, and to the investigators (in a blinded manner).

Any AE not listed as an expected event in the Reference Safety Information section of the Investigator's Brochure will be considered unexpected. Any worsening of or new onset of symptoms related to OA that occur during the screening period prior to study drug administration will be considered expected.

In addition, the sponsor will report all other SAEs to the health authorities, according to local regulations.

At the completion of the study, the sponsor will report all safety observations made during the conduct of the trial in the clinical study report to health authorities and ECs/IRBs as appropriate.

9.3. **Definitions**

9.3.1. Adverse Event

An AE is any untoward medical occurrence in a patient administered a study drug which may or may not have a causal relationship with the study drug. Therefore, an AE is any unfavorable and unintended sign (including abnormal laboratory finding), symptom, or disease which is temporally associated with the use of a study drug, whether or not considered related to the study drug.

An AE also includes any worsening (ie, any clinically significant change in frequency and/or intensity) of a pre-existing condition that is temporally associated with the use of the study drug.

9.3.2. Serious Adverse Event

An SAE is any untoward medical occurrence that at any dose:

- Results in **death** includes all deaths, even those that appear to be completely unrelated to study drug (eg, a car accident in which a patient is a passenger).
- Is **life-threatening** in the view of the investigator, the patient is at immediate risk of death at the time of the event. This does not include an AE that had it occurred in a more severe form, might have caused death.
- Requires in-patient hospitalization or prolongation of existing hospitalization. In-patient hospitalization is defined as admission to a hospital or an emergency room for longer than 24 hours. Prolongation of existing hospitalization is defined as a

hospital stay that is longer than was originally anticipated for the event, or is prolonged due to the development of a new AE as determined by the investigator or treating physician.

- Results in persistent or significant **disability/incapacity** (substantial disruption of one's ability to conduct normal life functions).
- Is a congenital anomaly/birth defect
- Is an **important medical event** Important medical events may not be immediately life-threatening or result in death or hospitalization, but may jeopardize the patient or may require intervention to prevent one of the other serious outcomes listed above. Examples of these include intensive treatment in an emergency room or at home for allergic bronchospasm; blood dyscrasias or convulsions that do not result in hospitalization; or development of drug dependency or drug abuse.

Criteria for reporting SAEs must be followed for these events. See Section 9.4 for more information on recording and reporting SAEs.

9.3.3. Adverse Events of Special Interest

An AESI (serious or non-serious) is one of scientific and medical concern specific to the sponsor's product or program, for which ongoing monitoring and rapid communication by the investigator to the sponsor can be appropriate. Such an event might warrant further investigation in order to characterize and understand it. Depending on the nature of the event, rapid communication by the trial sponsor to other parties (eg, regulators) might also be warranted (Section 9.4.3).

9.4. Recording and Reporting Adverse Events

9.4.1. Adverse Events

The investigator (or designee) will record all AEs that occur from the time the informed consent is signed until the end of the follow-up period (week 36)/early termination visit. Refer to the study reference manual for the procedures to be followed.

Information on follow-up for AEs is provided in Section 9.4.6. Laboratory, vital signs, or ECG abnormalities are to be recorded as AEs as outlined in Section 9.4.5.

9.4.2. Serious Adverse Events

All SAEs, regardless of assessment of causal relationship to study drug, must be reported to the sponsor (or designee) within 24 hours. Refer to the study reference manual for the procedure to be followed.

Information not available at the time of the initial report must be documented in a follow-up report. Substantiating data such as relevant hospital or medical records and diagnostic test reports may also be requested.

In the event the investigator is informed of an SAE after the patient completes the follow-up period (week 36)/early termination visit, the following will apply:

- SAE with an onset within 30 days of the end of the follow-up (week 36)/early termination visit the SAE will be reported to the sponsor. The investigator should make every effort to obtain follow-up information on the outcome until the event is considered chronic and/or stable.
- SAE with an onset day greater than 30 days from the end of follow-up period (week 36)/early termination visit only SAEs deemed by the investigator to be drug-related will be reported to the sponsor. The investigator should make every effort to obtain follow-up information on the outcome of a drug-related SAE until the event is considered chronic and/or stable.
- SAE reported by the patient at the end of the study phone call and deemed by the investigator to be drug-related will be reported to the sponsor. The investigator should make every effort to obtain follow-up information on the outcome of a drug-related SAE until the event is considered chronic and/or stable.

9.4.3. Other Events that Require Accelerated Reporting to Sponsor

The following events also require reporting to the sponsor (or designee) within 24 hours of learning of the event:

Symptomatic Overdose of Study Drug: Accidental or intentional overdose of at least 2 times the intended dose of study drug within the intended therapeutic window, if associated with an AE

Pregnancy: Although pregnancy is not considered an AE, it is the responsibility of the investigator to report to the sponsor (or designee), within 24 hours of identification, any pregnancy occurring in a female study patient during the study or within 20 weeks of the last dose of study drug. Any complication of pregnancy affecting a female study patient and/or fetus and/or newborn that meets the SAE criteria must be reported as an SAE. Outcome for all pregnancies should be reported to the sponsor.

Adverse Events of Special Interest: All AESI, serious and non-serious, must be reported within 24 hours of identification using the same reporting process as for SAE reporting per Section 9.4.2. Monitoring of AESIs is described in Section 9.6.1. Adverse events of special interest for this study include the following:

- Adjudicated arthropathy (as confirmed by adjudication)
- Joint replacement surgery (refer to Section 9.6.1.4 for when to report as an AESI)
- Sympathetic nervous system dysfunction (as diagnosed after consultation with an appropriate specialist, such as a neurologist and/or cardiologist)
- Peripheral sensory AEs that require a neurology or other specialty consultation

Refer to the study manual for the procedures to be followed.

9.4.4. Reporting Adverse Events Leading to Withdrawal from the Study

All AEs that lead to a patient's withdrawal from the study must be reported to the sponsor's Medical/Study Director within 30 days.

Refer to the study reference manual for the procedures to be followed.

9.4.5. Abnormal Laboratory, Vital Signs, or Electrocardiogram Results

The criteria for determining whether an abnormal objective test finding should be reported as an AE include:

- the test result is associated with accompanying symptoms, and/or
- the test result requires additional diagnostic testing or medical/surgical intervention, and/or
- the test result leads to a change in dosing (outside of protocol-stipulated dose adjustments), discontinuation from the study, significant additional concomitant drug treatment, or other therapy

Contact the Medical/Study Director in the event the investigator feels that an abnormal test finding should be reported as an AE, although it does not meet any of the above criteria.

Repeating an abnormal test, in the absence of any of the above conditions, does not constitute an AE. Any abnormal test result that is determined to be an error does not require reporting as an AE.

Evaluation of severity of laboratory abnormalities will be assessed according to the scale outlined in Section 9.5.1.

9.4.6. Follow-up

Adverse event information will be collected until the patient's last study visit.

Serious adverse event information will be collected until the event is considered chronic and/or stable.

9.5. Evaluation of Severity and Causality

9.5.1. Evaluation of Severity

The severity of AEs will be graded according to the following scale:

- **Mild:** Does not interfere in a significant manner with the patient normal functioning level. It may be an annoyance. Prescription drugs are not ordinarily needed for relief of symptoms, but may be given because of personality of the patient.
- **Moderate:** Produces some impairment of functioning but is not hazardous to health. It is uncomfortable or an embarrassment. Treatment for symptom may be needed.
- **Severe:** Produces significant impairment of functioning or incapacitation and is a definite hazard to the subject's health. Treatment for symptom may be given and/or patient hospitalized.

If a laboratory value is considered an AE, its severity should be based on the degree of physiological impairment the value indicates.

Injection Site Reactions

The severity of injection site reactions will be graded according to the following scale (semi-colon indicates "or" within description of grade):

- Mild: Pain that does not interfere with activity; mild discomfort to touch; <5 cm of erythema or induration that does not interfere with activity.
- **Moderate**: Pain that requires repeated use of non-narcotic pain reliever >24 hours or interferes with activity; discomfort with movement; 5.1 cm to 10 cm erythema or induration or induration that interferes with activity.
- Severe: Pain that requires any use of narcotic pain reliever or that prevents daily activity; significant discomfort at rest; >10 cm erythema or induration; prevents daily activity; requires emergency room visit or hospitalization; necrosis or exfoliative dermatitis.

9.5.2. Evaluation of Causality

Relationship of Adverse Events to Study Drug:

The relationship of AEs to study drug will be assessed by the "blinded" investigator, and will be a clinical decision based on all available information. The following question will be addressed:

Is there a reasonable possibility that the AE may have been caused by the study drug?

The possible answers are:

Not Related: There is no reasonable possibility that the event may have been caused by the study drug.

Related: There is a reasonable possibility that the event may have been caused by the study drug.

The investigator should justify the causality assessment of each SAE.

A list of factors to consider when assessing the relationship of AEs to study drug is provided below. Please note that this list is not exhaustive.

Is there a reasonable possibility that the event may have been caused by the study drug?

No:

- due to external causes such as environmental factors or other treatment(s) being administered
- due to the patient's disease state or clinical condition
- do not follow a reasonable temporal sequence following the time of administration of the dose of study drug
- do not reappear or worsen when dosing with study drug is resumed

Yes:

• could not be explained by environmental factors or other treatment(s) being administered

- could not be explained by the patient's disease state or clinical condition
- follow a reasonable temporal sequence following the time of administration of the dose of study drug
- resolve or improve after discontinuation of study drug
- reappear or worsen when dosing with study drug
- are known or suspected to be a response to the study drug based upon preclinical data or prior clinical data

Relationship of Adverse Events to Study Conduct

The relationship of AEs to study conduct will be assessed by the "blinded" investigator, and will be a clinical decision based on all available information. The following question will be addressed:

Is there a reasonable possibility that the AE may have been caused by study conduct?

The possible answers are:

Not Related: There is no reasonable possibility that the event may have been caused by study conduct.

Related: There is a reasonable possibility that the event may have been caused by study conduct.

The investigator should justify the causality assessment of each SAE.

A list of factors to consider when assessing the relationship of AEs to study conduct is provided below. Please note that the list if not exhaustive.

Is there a reasonable possibility that the event may have been caused by the study conduct?

Is there a reasonable possibility that the event may have been caused by the study conduct?

No:

- due to external causes such as environmental factors or other treatment(s) being administered
- due to the patient's disease state or clinical condition
- do not follow a reasonable temporal sequence following the course of the study
- do not reappear or worsen when dosing with study participation is resumed

Yes:

- could not be explained by environmental factors or other treatment(s) being administered
- could not be explained by the patient's disease state or clinical condition
- follow a reasonable temporal sequence following the course of the study
- resolve or improve after discontinuation from study participation.
- reappear or worsen when study participation is resumed

9.6. Safety Monitoring

The investigator will monitor the safety of study patient at his/her site(s) as per the requirements of this protocol and consistent with current Good Clinical Practice (GCP). Any questions or concerns should be discussed with the sponsor in a timely fashion. The sponsor will monitor the safety data from across all study sites. The Medical/Study Director will have primary responsibility for the emerging safety profile of the compound, but will be supported by other departments (eg, Pharmacovigilance and Risk Management; Biostatistics and Data Management). Safety monitoring will be performed on an ongoing basis (eg, individual review of SAEs) and on a periodic cumulative aggregate basis.

9.6.1. Monitoring Adverse Events of Special Interest

9.6.1.1. Adjudicated Arthropathy

Adjudicated arthropathy is an umbrella term that encompasses the following conditions:

- Rapidly progressive OA type 1 and 2
- Subchondral insufficiency fractures
- Primary osteonecrosis

In addition, adjudicated arthropathies will be evaluated to determine if they meet destructive arthropathy criteria.

Potential events of AA will be monitored via clinical signs and symptoms of worsening joint pain during the course of the study (eg, by applying adverse experiences, the joint pain questionnaire and imaging) as well as scheduled imaging and pre-operative imaging, if a patient requires a JR during the study.

Clinically significant worsening of joint pain during the course of this study is characterized as a worsening of pain in any joint that occurs in spite of treatment with analgesics, is in the opinion of the investigator inconsistent with the normal fluctuation of pain or progression of OA, and is at least 2 weeks duration (or less than 2 weeks if deemed clinically significant at the discretion of the investigator).

If a patient reports an increase in pain as described above, study drug administration will be withheld while imaging of the affected joint, as well as any additional imaging deemed appropriate to understand the cause of the worsening pain, is performed (Section 8.2.4.5). A decision to perform imaging after patient reported of worsening of joint pain will be documented in the respective CRF page. Images, along with any other radiographic evaluation, will be submitted to the arthropathy adjudication committee for review (Section 5.3.2). The investigator may consider aspiration of synovial fluid for further analysis such as cell count and crystal analysis.

If routine imaging suggests the presence of one of the types of AA, study drug administration will be withheld. Any additional imaging deemed appropriate will be obtained. The images, along with results of any other radiographic evaluation, will be submitted to the Adjudication Committee for review (Section 5.3.2).

If the adjudication does not confirm the presence of AA, according to the adjudication criteria, study drug may be restarted.

Study drug dosing will be permanently discontinued for patients with findings that suggest AA; the patients will be referred for orthopedic consultation. If presence of AA is confirmed by the Adjudication Committee, the case must be reported as an AESI (Section 9.3.3 and Section 9.4.3).

Any patient whose study drug is discontinued due to an AA should be encouraged to return to the clinic for all remaining study visits. If JR surgery is warranted, prior to the scheduled JR, the patient should complete the pre-operative study visit and, after the JR, should complete the week 4 and week 20 post-operative study visits (Table 2). Pre-operative images, along with any other radiographic evaluation will be submitted to the arthropathy adjudication committee for review (Section 5.3.2).

Details of data collection for adjudication of events will be provided in the adjudication charter.

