Data from studies of tanezumab and fulranumab indicated that these molecules were associated with an increased risk of destructive arthropathy (DA), a unique clinical form of rapidly progressive arthropathy over and above that seen in the normal progression of osteoarthritis. Analyses of the tanezumab data by its sponsor, defined by anatomic pathological criteria on specimens obtained on joint replacement (JR), revealed that the risk of DA increases with tanezumab dose and is further increased with the concomitant use of chronic NSAIDs (>90 days) (Lane 2010). Most cases of DA occurred in joints with a documented history of OA.

Based on the potential risk of DA identified in tanezumab and fulranumab, the US Food and Drug Administration (FDA) placed the class of anti-NGF antibodies on clinical hold in 2010. Following a review of anti-NGF antibody clinical data in March 2012, the FDA determined that clinical studies of anti-NGF therapies could resume if mitigation strategies were implemented to minimize

the risk of DA. To address concerns about potential events of DA, a risk-mitigation approach is also being implemented for all fasinumab studies, as outlined in Section 9.6.1.1. This approach includes sensitive, prospective, and rigorous radiologic screening and monitoring for select changes in joint structure. Patients who develop these changes, which are referred to throughout this document as adjudicated arthropathy (AA), are required to discontinue study therapy.

Since the removal of the FDA clinical hold, Regeneron Pharmaceuticals, Inc, (Regeneron) has conducted or initiated several clinical studies of fasinumab. In all clinical studies to date, fasinumab was associated with a low rate of discontinuations due to AEs. Patients treated with fasinumab generally had more frequent events than did placebo-treated patients of arthralgia, joint swelling, peripheral edema, altered peripheral sensation (eg, paresthesia, dysesthesia), and myalgia.

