7. STUDY TREATMENTS

7.1. Investigational and Reference Treatments

Fasinumab drug product is supplied for this study in the following concentrations:

- Fasinumab 2 mg/mL: Each 1 mL single-use pre-filled syringe delivers 0.5 mL of 2 mg/mL solution to provide a 1 mg dose of study drug
- Fasinumab-matching placebo: Each 1 mL single use pre-filled syringe delivers 0.5 mL of placebo solution.

All patients will receive SC injections of fasinumab or fasinumab-matching placebo. Patients will be randomized to 2 treatment groups in a 1:1 ratio to receive either fasinumab 1 mg SC Q4W or fasinumab-matching placebo SC Q4W. All SC injections will be in the abdomen, thigh, or upper arm. Instructions for dose preparation and study drug administration are provided in the pharmacy manual. Patients will be observed in the clinic for approximately 1 hour after study drug is administered.

Doses of study drug must be given within ± 7 days from the scheduled dose date. If the window is missed, the dose should not be administered. The next dose should be administered at the next scheduled dosing date.

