7.3.2.1. Reasons for Permanent Discontinuation of Study Drug

Study drug dosing will be permanently stopped in the event of:

- A patient developing clinically significant peripheral sensory or motor neurologic events confirmed by a neurologist's examination and graded by the neurologist as at least moderate peripheral neuropathy limiting activities of daily living, ie, grade ≥2 according to Common Terminology Criteria for Adverse Events (CTCAE) v.4; study sites should use CTCAE v.4 criteria throughout the study for consistency
- Evidence of pregnancy

- A patient developing signs and symptoms indicative of carpal tunnel syndrome
- Continued noncompliance with protocol-defined maximum acetaminophen/ paracetamol use (with a maximum daily dose of 2500 mg [countries where 500 mg strength tablets/capsules are available] or 2600 mg [countries where 325 mg strength tablets/capsules are available]) during the treatment and follow-up periods, after appropriate counseling
- Continued noncompliance with the protocol, including usage of NSAIDs or other medications or non-pharmacologic treatments that are not permitted in the study, after appropriate counseling
- JR surgery
- AESI:
 - Adjudicated arthropathy, as described in Section 9.6.1.1.
 - Sympathetic nervous system dysfunction, as described in Section 9.6.1.2.
- Per protocol repeated nerve conduction test that confirms results are not within the established parameters for peroneal, sural, or ulnar nerves, as per central reader assessment and the neurologist's evaluation that confirms the diagnosis of peripheral neuropathy.
- Hepatotoxicity. Study drug should be discontinued if the following are observed:
 - 1. Total bilirubin (TBL) >2x ULN or international normalized ratio (INR) >1.5, and
 - 2. ALT or AST >3x ULN, and
 - 3. No other cause for 1 and 2 is readily apparent

Other causes of ALT, AST, and TBL elevations may include alcoholic hepatitis, autoimmune hepatitis, non-alcoholic hepatitis, heritable diseases (Gilbert's Syndrome), heart failure, and viral hepatitis.

NOTE: Study drug may be withheld in patients who do not meet criteria for permanently discontinuing study drug, until an alternative cause for drug-induced liver injury can be determined. The patient may be re-challenged if an alternative cause for elevated liver function tests is found and the liver function tests return to baseline, but only after discussion with the sponsor.

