7.3.2.2. Reasons for Temporary Discontinuation of Study Drug

Study drug may be temporarily discontinued due to medical need, as determined by the investigator. Study drug will be temporarily withheld while awaiting imaging adjudication for worsening joint pain or when routine imaging suggests AA and prompts the need for additional imaging (see Section 9.6.1.1), for patients who are determined to have orthostatic hypotension or determined to have new or worsening symptoms suggestive of SNS dysfunction while awaiting evaluation by a specialist (see Section 9.6.1.2), or for patients with symptoms of peripheral neuropathy while awaiting evaluation by a specialist and/or results of a nerve conduction test (see Section 9.6.1.3).

Study drug should not be re-started until the next study visit, unless imaging, nerve conduction test results, or neurology evaluation results are available within the current visit window and confirm that study drug may be restarted.

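### Protocol 9.6.1.1 ties the permanent stop to suspected rather than confirmed arthropathy, against its own hold-and-restart rule (minor wording error)

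*Protocol*

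**What the plan says.** Protocol 9.6.1.1 sets out a sequence for suspected AA. For scheduled imaging: "If routine imaging suggests the presence of one of the types of AA, study drug administration will be withheld". Clinically significant worsening of joint pain also leads to a hold while the joint is imaged. Images from both routes go to the Adjudication Committee, and then: "If the adjudication does not confirm the presence of AA, according to the adjudication criteria, study drug may be restarted".

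Section 7.3.2.2 repeats this as a temporary measure: "Study drug will be temporarily withheld while awaiting imaging adjudication for worsening joint pain or when routine imaging suggests AA". On timing it adds "Study drug should not be re-started until the next study visit, unless imaging" or other specified results arrive within the current visit window and clear the patient. Section 7.1 allows ±7 days around each dose and says "If the window is missed, the dose should not be administered".

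The sentence in 9.6.1.1 that follows the restart rule reads: "Study drug dosing will be permanently discontinued for patients with findings that suggest AA". It also refers those patients for orthopedic consultation. The sentence after it makes Committee confirmation the condition for reporting the case as an adverse event of special interest (AESI).

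Elsewhere the permanent stop belongs to AA itself. The Introduction says of the joint changes found on radiologic monitoring: "Patients who develop these changes, which are referred to throughout this document as adjudicated arthropathy (AA), are required to discontinue study therapy". The list of permanent stopping reasons in 7.3.2.1 has the entry "Adjudicated arthropathy, as described in Section 9.6.1.1". Section 9.4.3 counts AA as an AESI only once adjudication has confirmed it.

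**The concern.** The same trigger, findings that *suggest* AA, leads to a reversible hold in one paragraph and an irreversible stop in the next. A site that follows the second paragraph to the letter would end treatment for a patient whom the Committee then finds not to have AA.

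Three things are at stake:

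- **Exposure.** The patient loses doses that the hold-and-restart rule would have allowed.
- **Efficacy data.** SAP 5.7.1 leaves WOMAC data collected after treatment discontinuation out of the main analysis. If the recorded reason is an adverse event, the replacement scores are centred at the baseline mean of the patient's treatment group; for other reasons outside lack of efficacy and death, they are imputed under missing at random.
- **Compliance.** SAP 5.6.4 summarises important protocol deviations and lists all of them. On the present text it is unclear whether restarting an unconfirmed case complies with the protocol.

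**Working it through.** The plan gives no figure to reproduce. The check is a comparison of text followed by a count of doses.

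**Step 1: the trigger and the action.**

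| Place in protocol | Trigger | Action |
|---|---|---|
| 9.6.1.1, hold paragraphs | Routine imaging suggests AA, or joint pain worsens significantly | Withhold; adjudicate; restart allowed if not confirmed |
| 7.3.2.2 | Same two triggers | Temporary hold |
| 9.6.1.1, next sentence | Findings that suggest AA | Permanent stop; orthopedic referral |
| 9.6.1.1, sentence after that | Committee confirms AA | AESI report |
| 7.3.2.1 | Adjudicated arthropathy, with a pointer to 9.6.1.1 | Permanent stop |
| Introduction | AA | Discontinuation required |
| 9.4.3 | AA confirmed by adjudication | AESI |

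Row 3 is the outlier. Its trigger is the one that rows 1 and 2 treat as temporary. Row 5 agrees with the other rows in naming adjudicated AA, but its pointer sends the reader back to the section containing row 3.

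**Step 2: which images can matter.** Doses fall at weeks 0, 4, 8 and 12 (Table 1). The last is due on day 85 and, with the ±7-day window, is given no later than day 85 + 7 = 92. The first scheduled post-baseline X-rays are at week 16, day 113, so no earlier than day 113 − 7 = 106; the next are at week 36. Scheduled imaging therefore leaves no dose to lose. X-rays at an early termination or pre-operative visit do not change this: the patient is leaving the study, or is having joint replacement, which is itself a permanent stopping reason in 7.3.2.1. What remains is in practice event-triggered imaging before the week 12 dose that looks suggestive and is later not confirmed. Worsening pain with unremarkable images never meets the disputed sentence.

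**Step 3: excess doses lost in such a case.** Let *r* be the doses remaining after onset and *h* the doses missed during the hold. A permanent stop loses *r*, hold-and-restart loses *h*, and the excess is *r* − *h*. The hold costs nothing if a negative result returns within the dosing window. It can cost every remaining dose if adjudication is slow. So *h* runs from 0 to *r*.

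| Onset (weeks) | Doses left | *r* | *h* | Excess *r* − *h* (of 4 doses) |
|---|---|---|---|---|
| 0-4 | weeks 4, 8, 12 | 3 | 0-3 | 0-3 |
| 4-8 | weeks 8, 12 | 2 | 0-2 | 0-2 |
| 8-12 | week 12 | 1 | 0-1 | 0-1 |

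**Step 4: the analyses.** The main WOMAC analysis drops data after discontinuation, while the treatment-policy sensitivity analysis in SAP 5.7.1 keeps them to week 16. The primary nerve-conduction analysis in SAP 5.8.1 also keeps them to week 16, so for that endpoint only exposure would change. Section 7.3.2 encourages patients who stop drug to complete all assessments.

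**The case against.** The strongest reply is that the disputed sentence directly follows the rule for an unconfirmed case and reads naturally as its complement: not confirmed, restart; otherwise, stop. The Introduction, 7.3.2.1, 7.3.2.2 and 9.4.3 all fit that reading. So do 7.3.2 and the later paragraph of 9.6.1.1, both of which speak of drug discontinued because of an AA. In 9.6.1.2 the protocol even uses *suggest* for a specialist's conclusion about sympathetic dysfunction, and there both the permanent stop and the AESI report depend on the specialist's positive finding.

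This stands as evidence of intent. A reader might infer that the protocol holds two genuinely competing stopping rules with no way to choose between them; the sections just cited do not support that. The reply does not rescue the sentence, however. Elsewhere in 9.6.1.1 and in 7.3.2.2, *suggests* describes imaging before adjudication. The following sentence introduces Committee confirmation as a separate condition and attaches it to AESI reporting alone.

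It is also fair to say that the literal reading errs toward stopping drug for a possible joint-safety event, so its cost is lost exposure rather than added risk. Restart is in any case only permitted, and the investigator may stop drug for any medical need.

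**Conclusion.** The sentence is wrong as written, and the point is minor. The permanent-stop trigger should be confirmed AA. For a suspected case arising before the week 12 dose and later not confirmed, the excess loss under the literal reading is 0-3, 0-2 or 0-1 of 4 doses by time of onset.

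Two stronger inferences are not supported:

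- A reader might infer minimum losses, with ranges of 2-3, 1-2 and 0-1 doses. Those hold only if adjudication always returns by the next dosing visit. The documents give no turnaround, so the lower limits of 2 and 1 cannot be kept.
- A reader might infer that the trial's results are affected. The documents do not give the number of suspected but unconfirmed cases or say how sites applied the sentence, so any effect on the main WOMAC analysis cannot be quantified. The primary nerve-conduction analysis retains the data to week 16.

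SAP 6.2 records that all patients had already had the chance to complete week 16. A correction now repairs the written rule and does not alter dosing in this trial.

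**What to change.** In the disputed sentence of Protocol 9.6.1.1, replace the description of the patients to be permanently discontinued with *patients with AA confirmed by the Adjudication Committee*. Leave the hold for suspected cases in 9.6.1.1 and 7.3.2.2 unchanged. Orthopedic referral stays in the same sentence and so attaches to confirmed AA, with earlier referral at the investigator's discretion. Making referral mandatory for every suspected case would add a requirement that the documents do not clearly intend.

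The cost is a wording change in a protocol amendment, which Section 15 requires an IRB or EC to approve, with regulatory approval where local rules call for it. No SAP change, new procedure or new data collection is needed.
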